#### Study Flow Diagram

### *Study Products*

AA-ORS is an amino acid–based, glucose-free, medical food/beverage that is lightly sweetened with stevia leaf extract. AA-ORS provides select amino acids and electrolytes (sodium and potassium)—nutrients intended to rebuild and protect the gastrointestinal tract and deliver hydration.

The AA-ORS for use in this trial, enterade®, will be commercially produced by Entrinsic Health Solutions, Inc. in accordance with US FDA standards for medical food products and good manufacturing practices. The AA-ORS will be used as supplied, meaning that other than packaging and labeling, there is no further study product preparation required. The corresponding placebo solution will be produced by Entrinsic Health Solutions for clinical trial use only.

In this study, AA-ORS and placebo solution will be formulated in bottles with 237 ml of clear liquid. All bottles will be clearly labeled as for research use only. Labels will meet all national and local requirements. The label must also include the product expiry date, batch number, and manufacture date.

The AA-ORS is stable at room temperature and has a 2-year shelf life when stored unopened in ambient temperatures below 25°C. Long-term (6-month) stability of the AA-ORS has also been demonstrated at 40°C with 65% relative humidity. The AA-ORS is stable for the entire study period, even at higher environmental temperatures that may be encountered in participants' homes during the study. The placebo solution is presumed stable. All study product not already dispensed to participants will be stored securely, only accessible to the study staff.

The study investigators will be required to maintain complete records of all study products received from the sponsor and/or manufacturer and will be responsible for maintaining an accurate record of the randomization codes and inventory and an accountability record for this study. The study investigators will also be responsible for ensuring the security of these documents, maintaining them under lock and key and/or electronic encryption.

At the completion of the study, the study investigators and site PI (or designee) will conduct and document a final reconciliation of all study product shipped, received, dispensed, consumed, and remaining. Any discrepancies identified will be investigated, resolved, and documented before any unused study product is destroyed. After all accounting and reconciliation procedures are complete and approved by the sponsor, all unused study product will be destroyed on site and documented in the master study files.

### *Study Procedures*

All IDI guides and data collection instruments will be pretested prior to data collection for gauging time required and flow of questions. IDI guides will be revised and adapted accordingly prior to data collection. Therefore, research assistant (RA) training will be composed of 1) review of guides and instruction on carrying out recruitment and consenting procedures, enrollment and interim questionnaires, weighing of children, and IDIs; 2) pretesting of IDI guides; and 3) revision/adaptation of guides with investigators, as necessary. RAs will field/pilot test the IDI and other questionnaires with a small number of caregivers in Kakamega, Kenya, before finalizing the instrument. Results from initial pretesting will be used to refine the data collection instruments before starting the study. Specifically, testing will be used to confirm target respondents are able to understand the questions being asked, that questions are understood in the same way by all respondents, and that respondents

are willing and able to answer questions. Table 4 presents an overview of data collection procedures and timing.

**Table 4.** Table of procedures (N=66 child/caregiver pairs).

	Screening	Enrollment (Day 1) *	Day 2	Day 4	Day 7		Day 14	Day 15	Day 21	Comments
Review of medical records for child eligibility	X									
Obtain consent		X								
Physical exam	X	X						X		
Blood draw (1–2 mL)		X						X		
Enrollment questionnaire (caregiver)		X								
Teaching caregiver to administer study product		X								
Direct observation of feeding		X								
AE assessment 30 mins after dose		X								
In-depth interview (caregiver)		X					X			
Supply product to home/pick up unused product			X	X#	X		X			
Review product administration with caregiver			X		X		X			
Text message to remind caregiver to start and stop study product			X	X	X		X			Twice daily during 2-week daily product administration.
Weight assessment	X				X		X			Done at the household, but may be done at the clinic, if needed.
Check in on adverse events; administer AE/interval medical history questionnaire		X		X	X		X			Done by study nurse in person on day 1, and then by phone all others.
Final recording of SAEs and close out of AEs									X	Done by study nurse, as needed, by phone or in person.
Report SAEs/SUSARs to regulatory entities		X	X	X	X		X	X	X	
*Enrollment will be at least 1 week post routine immunization, healthy child visit, or vitamin A supplementation visit at the study site, if recruited in-person rather than through CGH register review.										
#Day 4 is for pick-up of unconsumed product (bottles) only.										

Abbreviations: AE, adverse event; SAE, serious adverse event; suspected unexpected serious adverse reaction, SUSAR.

Screening visit:

During the screening visit, potentially eligible participants will be identified by clinic staff through the clinic records and routine information gathered at Expanded Program on Immunization (EPI)/Vit. A supplementation visits. Caregivers and their children will be referred to a study RA by clinic staff so the study RA can inform the caregivers about the study activities. Alternatively, potentially eligible children and their caregivers will come to the clinic after being identified from the CWC register and contacted by study staff (as described in *Recruitment and Consent Procedures*, below). As part of routine care, the child will receive a physical exam by a clinician or nurse. The routine physical examination conducted at EPI and Vit. A supplementation visits includes assessment of weight, weight categories (underweight, severe underweight, overweight, obese), height/length, stunted (stunted, severe stunted), and mid-upper arm circumference (MUAC) (green, yellow, red). If appropriate, the children identified from the CWC register will be given Vit. A supplements and any missing immunizations by clinic staff. If the caregiver is interested in participating in the study, he/she will be given a copy of the consent form and patient information leaflet to take home and review before coming back to the clinic for enrollment. In the case of an illiterate caregiver, the RA will confirm that there is at least one literate adult living in the child's household, and the RA will offer to read the consent form in full with the caregiver before sending the caregiver home. Any review of medical records prior to completion of informed consent will be done solely to identify potential participants for this study. Only data relevant to screening criteria will be recorded. If the caregiver declines enrollment in the study, any medical record data collected by study staff will be shredded and discarded.

Enrollment visit:

Upon return to the clinic ( $\geq 1$  week post screening visit) the RA will review the consent form with the parent or legally acceptable representative and answer any questions. The caregiver will be asked if they are still interested in continuing with participation in the study; if they agree, then the RA will complete the informed consent process and obtain their written signature on the consent form.

Once the consent form is signed and a copy has been given to the participant, the study nurse or clinician will conduct a medical examination, and a trained phlebotomist will draw blood from the child and collect a bloodspot on filter paper (see "Blood specimen collection and processing"). The RA will then proceed with the enrollment questionnaire and direct observation of the oral solution. For all children who join the study and are still breastfeeding, the enrollment questionnaire will include questions to establish a baseline breastfeeding rate (how many times a day). After direct observation of dosing with the solution, an RA will complete an IDI with the caregiver.

Training of caregivers

Caregivers will receive one 237-ml bottle of AA-ORS or placebo at enrollment along with a small cup and spoon to aid administration. The RA will train the caregiver to give the solution to their child and show them how to properly seal the bottle (containing unused solution) following solution provision (Appendix 6). The caregiver will administer the solution to their child in a private room in the clinic, under direct observation by an RA for 3 hours or until the solution has been finished, whichever comes first. Breastfeeding and solid feeding is permitted whenever desired during the 3-hour period.

Direct observation:

The goal of DOs is to directly witness the administration of AA-ORS or placebo solution and instruct caregivers to properly reseal bottles with unused solution. Target observations during the DOs include:

- Perceived palatability of study product by children.
- Perceived acceptable volume of study product by children.
- Ease of administration of study product by caregivers to their child.

Interim visits:

The following day after enrollment, the RA will visit the caregiver in their home to review the instructions and give the caregiver six additional 237-ml bottles. The RA will instruct the caregiver to give doses using the same technique and time limit used in the clinic for the next 20 days, to reseal unconsumed solution in bottles, and store bottles in a safe location (Appendix 6). The RA will help the caregiver to select an appropriate storage location for new and used bottles of AA-ORS/placebo that is out of reach of children and protected from heat and sunlight.

Each day during follow-up, an automated text message (SMS) will be sent to remind caregivers to administer the study product, and a second message (3 hours later) will remind them to mark and reseal bottles using tape and markers provided at enrollment. If automated SMS proves unfeasible, RAs will send SMS reminders to caregivers manually. The RA will visit the home on days 2, 4, 7, and 14 to collect unconsumed solution, review instructions, provide additional bottles (on day 2 and 7), and on days 7 and 14 only weigh the children. All empty or partial bottles will be collected, and unconsumed solution will be measured as part of the longitudinal volume feasibility assessment.

Interval medical history interviews:

Caregivers will receive study nurse contact information and can contact the nurse by phone at any time during the course of the study. Periodically during dosing (days 4, 7, 14, and 21) and 1 week after the end of dosing (day 21), a study nurse will contact the caregiver by phone and check in with the caregiver to assess any potential adverse events or serious adverse events, complete the routine interval medical history/stool frequency questionnaire, ask if the child is still breastfeeding (for children who were still breastfeeding at enrollment), answer any medical questions, and provide advice, as necessary. If breastfeeding has stopped, the caregiver will be asked if the child instituted the stoppage or if the mother decided to wean. All AEs and SAEs reported by the nurse will be reviewed by the study clinician, who will provide medical advice and care as needed.

Post-dosing visit:

Upon return to the clinic (within 3 days of the final dose) the study nurse or clinician will conduct a medical examination, and a trained phlebotomist will draw blood from the child and collect a bloodspot on filter paper (see "Blood specimen collection and processing"). After the medical examination and blood draw, an RA will complete an IDI with the caregiver. For all children who were still breastfeeding at baseline, the IDI will include questions to determine the breastfeeding rate (how many times a day) at the end of the study. The IDI will also assess whether breastfeeding has stopped in the prior week, and if so, if the child instituted the stoppage or if the mother decided to wean.

On day 21, a study nurse will contact the caregiver by phone for a final check-in with the caregiver to assess any potential adverse events 1 week after study product dosing ended.

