Study design:	This is a mixed-methods pilot study to assess the safety, acceptability, and feasible dosage of AA-ORS among children with mild to moderate stunting (LAZ between –1 and –3) who are at risk for EED and to assess the acceptability of this fluid supplementation for their caregivers. During the main study, child participants will be

randomized to receive 14 days of AA-ORS or placebo solution daily, dosing of up to 237 ml over a 3-hour period. Study staff and participants will be blinded to the study product allocation. Caregivers will store and return unused study product. Data collection methods to include direct observation of product consumption, adverse event assessments, structured surveys with caregivers, average daily volume consumed, and measurement of plasma/serum markers of metabolism, gut dysfunction, systemic inflammation, and micronutrient status pre- and post-administration of product.

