### iii. Study design, population, and study procedures

#### Study Approach and Study Population

To achieve the objectives listed above, we will closely monitor adverse events (AE) and serious adverse events (SAE) among study participants, conduct direct observations (DOs) and semi-structured in-depth interviews (IDIs) with potential end users (caregivers) in Kenya. IDIs will be undertaken to obtain an in-depth understanding of acceptability among end users (caregivers of pediatric patients 12–24 months of age) after AA-ORS use (post-deployment). The DOs will involve the study team observing initial administration of AA-ORS or placebo solution to a participating child. We will also gather and test blood samples in order to understand enteric dysfunction, systemic inflammation, and micronutrient deficiency in this child population.

The study population is 66 child/caregiver pairs. Eligible children will be 12–24 months of age without diarrheal or febrile illness, within the prior 7 days, who are experiencing mild to moderate stunting (LAZ between –3 and –1). Children with mild to moderate stunting at this age do not fall under the WHO guidelines for exclusive breastfeeding (< 6 months of age), are at increased risk for morbidity and mortality compared to children without stunting (13, 42), and may still be able to regain linear growth. That is, when children are under the age of 24 months, their growth is more plastic. Thus, stunting is more easily reversed than in older children. On an individual level, growth stunting is not always caused by EED, and those suffering from EED may not always have stunting. However, we have taken a practical or proxy case definition for “at risk for EED” based on stunting. This will allow us to determine how AA-ORS is tolerated in a population that at least overlaps considerably with true EED cases. Caregiver/child pairs will be enrolled and randomized into one of two groups receiving a daily dose of either (1) AA-ORS or (2) placebo solution (no amino acids) for 2 weeks, ad libitum over 3 hours up to 237 ml each day.

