5. Interim visits: RAs will visit the home on days 2, 4, 7, and 14 to collect unconsumed solution, review instructions, provide additional bottles (on days 2 and 7 only), and weigh the children (on days 7 and 14 only).
6. Adverse event check-ins: Periodically during dosing (days 4, 7, 14, and 21), and one week after the end of dosing (day 21), a study nurse will contact the caregiver by phone and check in with the caregiver to assess any potential AE or SAE, complete the routine interval medical history (with feeding and breastfeeding assessment)/stool frequency questionnaire, answer any medical questions, and provide advice, as necessary.
7. On the fifteenth day of follow-up (or within 2 days after), following the 2-week dosing period, patients and their caregivers will return to the clinic for medical evaluation, collection of blood samples, and caregiver IDIs. Samples will be processed and stored for laboratory analyses following the same procedures from the enrollment blood collection.

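### The day-2 home instruction is to dose for 20 more days, giving 21 doses in a 14-day course, and the unstated day-7 bottle count does not cap it

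*Combined protocol and SAP*

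**What the plan says.** The intended course is 14 days. The Study Overview, the sample size table, the objectives and the analysis section all give 14 days or two weeks. Study Approach and Study Population has children dosed "for 2 weeks, ad libitum over 3 hours up to 237 ml each day". Key Activities item 7 places the day-15 clinic visit after the two-week dosing period. The Post-dosing visit text describes the day-21 call as "a final check-in with the caregiver to assess any potential adverse events 1 week after study product dosing ended".

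The operative instruction differs. At the home visit on day 2, under Interim visits in Study Procedures, the research assistant is to tell the caregiver to "give doses using the same technique and time limit used in the clinic for the next 20 days".

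On supply, Training of caregivers says "Caregivers will receive one 237-ml bottle of AA-ORS or placebo at enrollment", and on day 2 the research assistant is to "give the caregiver six additional 237-ml bottles". Key Activities item 5 and Interim visits allow one later delivery, on day 7, with no number of bottles. The Table 4 row "Supply product to home/pick up unused product" is marked on day 14, and the Study Overview adds: "Caregivers will store and return unused study product".

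Other text also fits 21 doses better than 14:
- Safety Monitoring (section C.x) numbers the bottles 1 to 21.
- Key Activities item 6 and the interval medical history text list day 21 among the calls made during dosing, and in the same sentence as one week after it.
- Data Analysis Procedures puts the between-arm biomarker test at day 22.

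**The concern.** The day-2 sentence is what staff say to the person giving the doses, and it covers all 13 home doses of the intended course. A caregiver acts on that, not on the objectives or the sample size table. If dosing ran past day 14, four parts of the safety and exploratory design would be affected:

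- Doses would be given after the last home weighing (day 14) used for the 5% weight-loss rule. The only later weight is at the day-15 examination.
- The examination and blood draw planned as post-dosing could fall mid-course.
- The final call would not give the seven days of post-dosing safety follow-up set in Reporting Period and Parameter.
- Cumulative exposure would exceed plan in a trial whose first primary objective is safety. Table 7 notes that earlier safety data come from adults and may not carry over to children.

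The day-22 biomarker test is a separate but related error, because it names a day with no sample.

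**Working it through.** **Doses instructed against doses planned**

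- Planned: 14 daily doses, days 1–14 (Study Overview). One is given in clinic, so 14 − 1 = 13 are given at home.
- Instructed on day 2: 20 more days. Counting from day 2, the last dose is on day 2 + 20 − 1 = 21, and the total is 1 + 20 = 21.
- If the 20 days were counted from day 3, the last dose would be on day 3 + 20 − 1 = 22. Neither reading gives 14.
- Excess over plan: 21 − 14 = 7 doses, and 21/14 = 1.50.

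**Does supply cap the course?**

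- Bottles provided by day 2: 1 + 6 = 7, covering days 1–7.
- With *b* bottles delivered on day 7, total doses = 7 + *b*, and at one a day the last dose is on day 7 + *b*.
- A 14-dose course needs *b* = 14 − 7 = 7. A 21-dose course needs *b* = 21 − 7 = 14.
- The protocol does not state *b*.

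**Consequences by day-7 bottle count**

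The final call is on day 21 or up to three days later (Reporting Period and Parameter). Post-dosing follow-up is therefore 21 − (7 + *b*) to 24 − (7 + *b*) days. Maximum volume is 237 × (7 + *b*) ml. The middle row is an illustrative value that does not come from the documents.

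| Bottles on day 7 | Doses | Maximum volume | Relative to 3,318 ml | Follow-up after last dose |
|---|---|---|---|---|
| 7 | 14 | 14 × 237 = 3,318 ml | 1.00 | 7–10 days |
| 10 | 17 | 17 × 237 = 4,029 ml | 1.21 | 4–7 days |
| 14 | 21 | 21 × 237 = 4,977 ml | 1.50 | 0–3 days |

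The excess in the last row is 7 × 237 = 1,659 ml. These are cumulative maxima. The daily maximum stays at 237 ml and intake is ad libitum.

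**Timing of the post-dosing visit with 14 bottles**

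The visit is on day 15 or up to two days later. On day 15, before that day's dose, days 15–21 remain: 7 doses. On day 17, after that day's dose, days 18–21 remain: 4 doses. So 4–7 doses would still be to come.

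**Day 22**

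Blood Specimen Collection and Processing and Key Activities give two draws only, at enrollment and at the day-15 visit. The exploratory endpoint is also defined at baseline and day 15. A day-22 comparison cannot be run as written. Day 22 follows a 21-dose course as day 15 follows a 14-dose course, which suggests an earlier 21-day schedule. That is an inference, and the contradictions stand without it.

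**The case against.** The strongest reply is that the intent is plain and the harm remote. Fourteen days is stated throughout, and the Post-dosing visit text places the day-15 visit no more than three days after the last dose, which fits only a last dose around day 14. For over-dosing to occur, the instruction must be followed, more than seven bottles must be delivered on day 7, and nobody must notice. There are several chances to notice: review of administration with the caregiver on days 7 and 14 (Table 4), the nurse's day-14 call, the day-14 collection, the day-15 visit and the independent monitor's visits. Table 4 limits text reminders to the two-week course. The bottle numbers concern labels and do not establish how many bottles are dispensed. The protocol also expects minimal risk, sees no prior reason for a safety concern, and reports no adverse events in a study of five children. Day 15 is clearly meant for the biomarker test.

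Most of this stands, and it bears on how likely over-dosing is. It does not remove the contradiction, because these checks would be catching an error that the protocol itself instructs. Nor are they all firm: Interim visits sends reminders on every day of follow-up, which is looser than Table 4, and the 1-to-21 numbering means a seven-bottle delivery on day 7 cannot be taken for granted. Five children is thin reassurance. The caregiver sheet (Appendix 6) is not in the text available, so what caregivers would read at home cannot be judged.

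**Conclusion.** The concern holds. The protocol instructs 21 doses in a 14-day course. That follows from counting and rests on no assumption.

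The consequences are conditional. They require that the instruction is followed, that more than seven bottles are supplied on day 7, and that the day-14 and day-15 contacts do not catch it. At 14 bottles, with every bottle finished, the excess is 7 doses or 1,659 ml (+50%), with 0–3 days of post-dosing follow-up and 4–7 doses outstanding at the visit meant to follow dosing. At seven bottles there is no excess.

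The daily cap and the 14-day volume endpoint are unaffected. Both arms receive the same instruction, so it does not by itself bias the between-arm adverse event comparison. The day-22 test is wrong as written, though its intent is clear. This should be corrected, but it is not a flaw in the design.

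**What to change.** - Interim visits (Study Procedures): replace the 20 days with the next 13 days, days 2–14. This gives 1 + 13 = 14 doses, puts day 15 one day after the last dose and puts day 21 seven days after it.
- Key Activities item 5 and Interim visits: state that seven bottles are given on day 7 and none on day 14. The second part is worth saying because Table 4 combines supply and pick-up in one row marked on day 14.
- Safety Monitoring: number the bottles 1–14.
- Key Activities item 6 and the interval medical history text: list days 4, 7 and 14 as the calls during dosing, and day 21 only as the call one week after it.
- Interim visits, text reminders: limit them to days 2–14, in line with Table 4.
- Data Analysis Procedures, exploratory endpoint: change day 22 to day 15.
- Check the caregiver sheet (Appendix 6) and the bottle labels against these figures before staff training.

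The cost is a handful of wording corrections and one document check. Design, sample size and visits do not change.
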